6.3 Criteria for withdrawal/discontinuation of participants

There are several situations in which the participant may be withdrawn from the study, including the development of an exclusion criterion during the execution of the study, withdrawal of informed consent, and when the participant is unwilling to continue the study.

The withdrawn participants do not have to be replaced.

If the participant withdrawals from the study, his/her data must be anonymized at the end of the study. This anonymization is not performed if the participant gives explicit consent. For the protection of the withdrawn participant, he/she must be provided with the standard follow-up care designated by his/her respective medical professional.

7 Statistical analysis plan and power calculation

Machine learning models are data-hungry models. This means that the performance of the model will potentially increase with the increase of the dataset and classified events in each classification class. We could simplify the classification task by categorizing alarms as relevant or irrelevant, thus reducing it to a binary classification problem. We will probably have to deal with an unbalanced problem as we might receive a lot of irrelevant classified alarms and few relevant ones. In an unbalanced classification problem as in our case, the best measurements to assess model performance are precision and sensitivity. Precision is defined as the fraction of well-classified instances from class A among all instances that were classified as class A. Sensitivity instead is defined as the fraction of instances from class A that were classified as pertaining to class A. A recent study by Juba and Le (Juba and Le, 2019) proved that even using data augmentation techniques to deal with an unbalanced dataset, adding more training data is the best solution for measuring precision and recall.

Furthermore, we pretend to train the algorithm not just to solve the binary classification problem but also to be able to give specific recommendations in terms of changes in medication, hospital readmissions, and others. Thus, the sample size might have to be big enough to cover a huge range of possible outcomes.

For instance, a similar study (Koulaouzidis et al., 2016) with 308 HF patients telemonitored for around 9 months predicted whether patients would undergo hospital readmission during the following day based on the day-to-day physiological measurements of each patient. Performance accuracy was high. However, more specific measures such as the sensitivity were very low, putting patients at a high risk of misclassification.

During model development and training, k-fold cross-validation will be implemented to fine-tune the model parameters and ensure robustness. Additionally, part of the data won't be used during training and validation in order to test model performance on new data never seen by the algorithm. After the implementation of the AI system into the platform, a randomized controlled trial will be carried out in hospitals that didn't participate in the present observational study to externally validate the ML models. In this future study, a quantitative sample size evaluation will be possible by comparing clinical outcomes between the control and study group.

Therefore, the sample size for the present study has been determined qualitatively taking into consideration the reasons mentioned above, that during the 3 first months after HF decompensation is when patients present more harmful events, and the budget available for the project. The plan is to include the maximum number of participants while accomplishing a relevant socio-demographic diversity in the final cohort. We consider that a total of 500 patients will give sufficient data diversity and classified events (alarms + unexpected interventions) to ensure a robust model performance.

Once the algorithms are developed, model performance in terms of accuracy will be evaluated by means of C statistic, the area under the receiver operating characteristic curve, and by creating a calibration plot. Furthermore, we will evaluate the models in terms of fairness and potential bias using metrics such as statistical parity, group fairness, equalized odds, and predictive equality.

8 Conduct

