5.2 Primary and secondary endpoints

Primary endpoints

- Creation of a labeled and diverse dataset from a multicenter perspective. The dataset will contain the following data:
 - Physiological parameters: heart rate, calories consumed, steps count, physical activity, oxygen saturation, heart rate variability measurements, stress levels, sleep tracking data, systolic and diastolic blood pressure, weight, BMI
 - Socio-demographic data: sex, age, ethnic group, employment, level of education, number of people living with the patient, caretaker.
 - Risk factors: comorbidities, diabetes, hypertension, smoking, alcohol consumption, heart disease history
 - Medication tracking: lipid-lowering medication, PCSK9 inhibitors, beta-blockers, anticoagulation agents, ACE inhibitors, anti-arrhythmic drugs, anti-inflammatory drugs, aldosterone antagonists, angiotensin receptor/neprilysin inhibitor, other diuretics
 - Symptomatology questionnaire for patients
 - NYHA-class
 - Left Ventricular Ejection Fraction (LVEF)
 - Clinical interventions: hospital readmission, mortality, UCI visits
 - Health questionnaire answers: self-care, quality of life
 - Classified alarms with their respective timestamp and annotation by the medical professionals
 - Measurement ranges for each personalized alarm and their changes

- Implementation of ML models to improve the current alarm-based system using the dataset created. The models should:
 - Provide a relevance level for each new alarm by reducing the number of irrelevant alarms and thus fostering personalized follow-up.
 - Be robust across different new hospitals and reliable and fair across different target populations, considering the diverse sociodemographic data that will be available in the dataset.

Secondary endpoints

- Development and implementation of ML event prediction algorithms that will add new self-generated alarms to the system. These alarms should forecast:
 - Untracked hospital interventions, such as UCI visits or hospital readmissions.
 - Changes of medication with their particular estimated dose.
 - Clinical events, such as mortality.
- Assessment of patient and medical professional's satisfaction with and usability of the digital platform at the end of the study by means of the "System Usability Scale" (SUS) (Brooke, 1986) and the "Post-Study Usability Questionnaire" (PSSUQ).

6 Subjects/population(s)

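### Section 5.2 makes robustness in new hospitals part of a primary machine-learning endpoint, but Section 7 defines no split and no result by hospital for this study

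*Combined protocol and SAP*

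**What the plan says.** Section 5.2 has two primary endpoints. The first is "Creation of a labeled and diverse dataset from a multicenter perspective". The second is the implementation of models that improve the alarm system, and one of its two requirements is that they "Be robust across different new hospitals and reliable and fair across different target populations". Synopsis endpoint B leaves this requirement out.

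Section 7 holds the analysis plan. For this study it states:

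- **Tuning:** "k-fold cross-validation will be implemented to fine-tune the model parameters and ensure robustness". Neither the number of folds nor the unit that defines a fold is given.
- **Testing:** a share of the data is kept out of training and validation "in order to test model performance on new data never seen by the algorithm". Neither its size nor its unit is given.
- **Measures:** the C statistic, "the area under the receiver operating characteristic curve, and by creating a calibration plot".
- **Fairness:** four group metrics. The groups are not defined, and Section 5.2 ties this aim to sociodemographic data, not to hospital.

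For later, Section 7 says: "After the implementation of the AI system into the platform, a randomized controlled trial will be carried out in hospitals" that did not "participate in the present observational study to externally validate the ML models". For that trial, "a quantitative sample size evaluation will be possible by comparing clinical outcomes between the control and study group".

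**The concern.** Data the algorithm has not seen need not come from a hospital it has not seen. Unless folds or the hold-out are formed from whole hospitals, each test patient will almost certainly come from a hospital that also supplied training patients. Such a test cannot show how the model behaves elsewhere.

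The documents give one concrete way in which hospitals differ in their patients. Under Section 6.2 each site chooses whether to enrol at discharge planning or at a first visit one or two weeks later. Alarm labels are judgements by medical professionals (Section 8.2.1), so different labelling by site is plausible, though not stated.

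At stake is what the final report can claim. It could show good pooled discrimination and a good calibration plot and call the endpoint met, with no evidence on its new-hospital part. Poor transport would then first appear in the later trial, after implementation.

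**Working it through.** **No figure in the plan to reproduce.** The 500 patients were chosen qualitatively, and the synopsis states that there is no power calculation. The number and size of hospitals are not in the available text.

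**Step 1. Can an ordinary random split contain an unseen hospital?** Inputs: 500 patients (Section 5.1); hold-out of h patients and hospital of n patients (both assumed). The chance that all n patients fall in the hold-out is

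P = C(500 − n, h − n) / C(500, h).

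| n | h = 50 (10%) | h = 100 (20%) | h = 150 (30%) |
|---|---|---|---|
| 5 | 8.3e-6 | 0.00029 | 0.0023 |
| 10 | 4.2e-11 | 7.0e-8 | 4.8e-6 |

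For H equal hospitals, the expected number wholly unseen is H × P. With 25 hospitals of 20 and a 30% hold-out it is 3.4e-10. With 50 hospitals of 10 and 30% it is 50 × 4.8e-6 = 0.00024. A random patient-level hold-out therefore tests known hospitals only.

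**Step 2. Could results by hospital come from the hold-out alone?** With 5 to 25 equal hospitals and a 10% to 30% hold-out, the mean is between 50/25 = 2 and 150/5 = 30 test patients per hospital. Results by hospital are better taken from cross-validated predictions on all 500.

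**Step 3. How much might it matter?** This is an illustrative simulation in which every input except the 500 patients is assumed. It used 10 hospitals of 18 to 86 patients, 30 alarms per patient, a patient SD of 1.0 on the logit scale and about 22% to 25% relevant alarms. Hospital intercept SD/slope SD was none, 0.5/0.3 (middle) or 0.8/0.5 (strong).

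| | None | Middle | Strong |
|---|---|---|---|
| Mean within-hospital AUROC, patient folds minus leave-one-hospital-out: boosting | −0.002 | 0.004 | 0.014 |
| Same: logistic | −0.001 | 0.005 | 0.014 |
| Mean minus worst AUROC over left-out hospitals: boosting | 0.039 | 0.078 | 0.129 |
| Same: logistic | 0.032 | 0.088 | 0.134 |
| Lowest to highest observed/expected, hospitals left out: boosting | 0.86–1.22 | 0.57–1.74 | 0.44–2.02 |
| Same: logistic | 0.82–1.19 | 0.55–1.57 | 0.41–1.80 |

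- **The mean moves little.** With 5 hospitals the logistic differences were 0.012 (middle) and 0.030 (strong); with 20 hospitals they were 0.001 and 0.006.
- **Part of the worst-hospital gap is noise.** The no-effect column is sampling noise only. Its share of the gap is 0.039/0.078 = 50% and 0.039/0.129 = 30% for boosting, and 0.032/0.088 = 36% and 0.032/0.134 = 24% for logistic.
- **Pooled calibration does not reveal the spread.** For the logistic model, pooled observed/expected was 1.00 in all three settings under either scheme.
- **Most of the spread shows without leaving hospitals out.** In a logistic run with similar settings, observed/expected by hospital ranged from 0.55 to 1.45 with patient-level folds against 0.52 to 1.58 with hospitals left out (middle), and 0.41 to 1.62 against 0.38 to 1.85 (strong). The ratios of the widths are 0.90/1.06 = 85% and 1.21/1.47 = 82%. Worst-hospital AUROC for boosting, middle setting, was 0.590 against 0.593.

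**The case against.** The strongest reply is that new hospitals means hospitals outside this study, and that Section 7 already assigns that test to a later trial. Section 4.1 divides the work in the same way: this study builds the dataset and develops the algorithms, and a second study validates them. On this reading only a cross-reference is missing. Part of this stands. A reader might infer that the models would never be tested in new hospitals, or that a hospital-level split is excluded. Neither follows: the test is announced for later, and the split unit is unspecified, so whole hospitals could be held out. What does not stand is that the later trial settles this study's endpoint. Section 5.2 lists the requirement here without deferring it, and the trial follows implementation.

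A second reply is that the simulation assumes its hospital differences. That is correct, and it shows only what could be missed. A reader might also infer that pooled AUROC would be materially inflated. The runs do not support this: the mean shift with 10 hospitals is about 0.00 to 0.015. They support reporting by hospital more strongly than leaving hospitals out.

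Third, feasibility is unknown, because the number and size of hospitals are not available. This stands, and the fix allows for it.

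**Conclusion.** The point holds in a limited form. Section 5.2 places robustness in new hospitals under a primary endpoint, and none of the analyses written for this study addresses it: no fold, hold-out, performance measure or fairness group is defined by hospital. If the split is random by patient, which is an assumption, the chance that a given 10-patient hospital is unseen is at most about 5e-6 for hold-outs up to 30%. This rests on the documents and on exact arithmetic and does not need the simulation.

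The practical size is uncertain. It depends on how far hospitals really differ, and the only documented difference bearing on patients is the timing of inclusion. The likely harm is unseen spread between hospitals, mainly in calibration, and not a large bias in the mean AUROC. The plan should be changed before analysis. The gap does not undermine the creation of the dataset, and external validation is already announced.

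**What to change.** In Section 7:

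1. Report AUROC, calibration, precision and sensitivity by hospital, from cross-validated predictions on all patients. Summarise the between-hospital spread with a random-effects model, so that sampling noise is not read as a hospital difference. This is the better supported change.
2. Add leave-one-hospital-out (internal-external) cross-validation, with tuning inside the training hospitals and small sites grouped. Keep all data of a patient on one side of every split.
3. Confirm that the hospital identifier is kept in the analysis dataset. Neither Table 1 nor the day-0 variables list it, although it is probably recoverable from registration on the platform.

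If the number or size of hospitals makes item 2 infeasible, state in Section 5.2 that robustness in new hospitals will be tested in the later trial, and do not claim it from this study. Use the same wording in synopsis endpoint B.

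The cost is plan wording and computing time, with no extra patients, and no extra data provided the identifier is available. Figures for small hospitals will be imprecise, and estimates will probably be somewhat lower. Leave-one-hospital-out also evaluates the modelling procedure, not the single final model, and the report should say so.

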| | 
 • Patients who do not use Catalan, Spanish, English, Portuguese, Italian, Dutch, German, Swedish, Hungarian, Romanian, or French. • Patients without a mobile phone • Patients without internet connection • Patients with moderate or severe cognitive impairment without a competent caregiver. • Patients with severe psychiatric illness. • Patients with planned cardiac surgery. • Patients with planned heart transplant or LVAD implant. |
| Recruitment strategy: | When a patient is eligible according to the criteria, he/she must complete the informed consent provided on day 0. Each hospital will decide when to include their patients according to their particular clinical practice (either in the process of discharge planning or during the first follow-up visit, i.e.. 1 or 2 weeks after discharge). Patients will be monitored for 6 months, with a recruiting period of 6 months. The last subject included will then finish the study after one year from the first day of the study. |
| Data Analysis: | There is no power calculation associated with the study since it is an observational study. Once the algorithms are developed, model performance in terms of accuracy will be evaluated by means of C statistic, area under the receiver operating characteristic curve, and creation of a calibration plot. Furthermore, the models will be evaluated in terms of fairness and potential bias using metrics including statistical parity, group fairness, equalized odds, and predictive equality. |
| Study Schedule: | February - March 2023: CEIm approval April 2023: study kick-off October 2023: recruitment period completed. April 2024: last patient, last visit May 2024: results analysis and final report draft |

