4.1 Background and rationale

Heart Failure (HF) is a prevalent and fatal clinical syndrome that affects the quality of life of millions of people worldwide. Between 17% and 45% of patients suffering from HF die within the first year and the remaining die within 5 years (Tripoliti et al., 2017). Furthermore, those patients have a high risk of rehospitalization, their associated healthcare costs are huge, and the higher the life expectancy, the higher the disease's prevalence (McDonagh et al., 2021). HF symptoms commonly include shortness of breath, excessive tiredness, and leg swelling which may be worsened with decompensation (Schiff et al., 2003), and thus displacement to medical centers represents a handicap for such individuals. Remote monitoring technologies provide a feasible solution that allows earlier decompensation identification and better adherence to lifestyle changes and medication (Brahmbhatt & Cowie, 2019). Although telemonitoring by smartphones showed the potential to reduce both the frequency and the duration of HF hospitalizations (Koulaouzidis et al., 2016; Scherr et al., 2009), there was no association with the reduction of all-cause mortality (Koehler et al., 2011). Thus, it indicates there is a need to look for more effective and precise methodologies. In recent years, the use of wearable devices that allow daily monitoring of patient's physiological data combined with Artificial Intelligence (AI) has shown immense potential in predicting cardiovascular-related diseases, their adverse events and patient's health status (Lee et al., 2022), including that of patients with HF (Guidi et al., 2015).

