6.2 Recruitment and screening

For the creation of the dataset, many hospitals have been contacted. Patients will be included in the study based on the eligibility criteria mentioned and must complete the informed consent provided on day 0. Patients will be monitored for 6 months after being included in the study on day 0. Each hospital will decide when to include their patients according to their particular clinical practice (either in the process of discharge planning or during the first follow-up visit, i.e.. 1 or 2 weeks after discharge).

The recruitment period is defined as 6 months. That means patients will be incorporated into the study from its start until the sixth month. The last subject included in the study will then finish the study after one year from the first day of the study (study KICKOFF: first patient - first day).

Medical professionals from each hospital will be in charge of recruiting the participants. The recruitment rate is specific for each hospital, and it may vary depending on the month.

If the recruitment target is not reached for a specific center at the end of the recruitment period (6 months), the latter may be extended until the accorded number of participants recruited is satisfied under the hospital decision.

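### The assurance that 500 patients suffice has no quantitative support, and one hold-out of usual size would test the mortality forecast on too few deaths

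*Combined protocol and SAP*

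**What the plan says.** **Sample size.** The synopsis (Data Analysis) says: "There is no power calculation associated with the study since it is an observational study". Section 7 adds that "the sample size for the present study has been determined qualitatively taking into consideration the reasons mentioned above". Those reasons are class imbalance, the range of outcomes to be covered, the concentration of events early after decompensation, and the budget. It then concludes that "a total of 500 patients will give sufficient data diversity and classified events (alarms + unexpected interventions) to ensure a robust model performance".

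**Comparator.** Section 7 cites a similar study "with 308 HF patients telemonitored for around 9 months predicted whether patients would undergo hospital readmission during the following day" from daily measurements. Accuracy was high. "However, more specific measures such as the sensitivity were very low, putting patients at a high risk of misclassification". No sensitivity value or event count is given. The same section names precision and sensitivity as the best measures for an unbalanced problem of this kind.

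**Testing.** k-fold cross-validation is planned for tuning and robustness. Separately, part of the data is set aside "in order to test model performance on new data never seen by the algorithm". Neither its size nor the unit of the split (patient, hospital or record) is stated. A randomized trial in other hospitals is to validate the models externally, after the system has been built into the platform.

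**Targets.** Section 5.2 lists forecasts that are to become new alarms: hospital interventions, medication changes with dose, and clinical events, with mortality as the example.

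**The concern.** The conclusion about 500 patients reads as a property of the design, yet no number stands behind it. The one benchmark in the section points the other way on the measure the plan prefers, and its monitored time was close to what this study will collect.

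The practical problem lies in the test step. For a rare target, the precision of sensitivity depends on the number of events in the test data, not on the 500 patients. If the held-out part contains only a handful of deaths, the reported sensitivity cannot separate a poor mortality forecast from a good one. Section 5.2 would turn that forecast into an alarm, and Section 7 places implementation before the external trial. The internal estimate is therefore the only planned evidence of performance at that point.

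**Working it through.** The figure of 500 cannot be reproduced. The documents give no target precision, expected event count, hold-out fraction or dropout rate. What can be checked is set out below.

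**Inputs from the documents.** 500 patients (Section 7). Follow-up: "Patients will be monitored for 6 months after being included in the study on day 0" (Section 6.2). Comparator: 308 patients, about 9 months (Section 7). Mortality: "Between 17% and 45% of patients suffering from HF die within the first year" (Section 4.1), the only clinical event rate given.

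**Assumptions.** Constant hazard; the general mortality range applies to this cohort; hold-out of 10%, 20% or 30%, split by patient; sensitivity near 0.80, with each death counted once.

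**1. Gross monitored time.** Comparator: 308 × 9 = 2,772 patient-months. This study: 500 × 6 = 3,000. Ratio 3,000 / 2,772 = 1.08. There are 500 / 308 = 1.62 times as many patients, but only 8% more monitored time.

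**2. Expected deaths by 6 months.** Risk = 1 − (1 − annual risk)^0.5.
- 17% per year: 1 − 0.83^0.5 = 0.089; × 500 = 44 deaths.
- 45% per year: 1 − 0.55^0.5 = 0.258; × 500 = 129 deaths.

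**3. Deaths available for testing, with exact (Clopper-Pearson) 95% intervals for sensitivity near 0.80.**

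| Test data | Deaths at 17%/yr | Interval | Deaths at 45%/yr | Interval |
|---|---|---|---|---|
| 10% hold-out | 4 | 0.19–0.99 (3/4) | 13 | 0.46–0.95 (10/13) |
| 20% hold-out | 9 | 0.40–0.97 (7/9) | 26 | 0.61–0.93 (21/26) |
| 30% hold-out | 13 | 0.46–0.95 (10/13) | 39 | 0.64–0.91 (31/39) |
| All 500, out-of-fold | 44 | 0.65–0.90 (35/44) | 129 | 0.72–0.86 (103/129) |

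For an assumed C statistic of 0.75 (Hanley-McNeil standard error), the 95% half-width is 0.19 to 0.12 with a 20% hold-out, and 0.09 to 0.05 with all 500.

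**4. Yardstick.** A half-width of 0.10 at sensitivity 0.80 needs 1.96² × 0.8 × 0.2 / 0.1² = 61.5, so 62 deaths. That is 62 / 0.089 = 697 test patients at 17% per year, more than the cohort, or 62 / 0.258 = 240 at 45% per year, 48% of it. No hold-out in the table reaches 62.

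**5. Early clustering.** If the 6-month risk were double, a 20% hold-out would contain 2 × 8.9 = 18 to 2 × 25.8 = 52 deaths, still under 62. A 30% hold-out would contain 27 to 78, so the top of the range would pass.

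**6. Commoner events.** The documents give no readmission rate. At assumed 6-month risks of 15%, 25% and 40%, a 20% hold-out has 15, 25 and 40 patients with an event. At 40% risk and a 30% hold-out there are 60 (interval 0.68–0.89), close to the yardstick. So the shortage is not shown for readmission.

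**The case against.** **The comparator does not refute the plan.** A reader might infer that the cited study contradicts the claim about 500 patients. The documents do not support that. It forecast next-day readmission only, and no event count, threshold or sensitivity value is given. Its low sensitivity may come from the one-day horizon or the threshold rather than from size. The plan cites it as a reason for collecting more data, which is consistent with its argument. It also has more patients, which matters for diversity, and enrols within 30 days of a decompensation, when it expects more events. This all stands. The near-equal patient-time shows only that the comparator lends the assurance no support.

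**Net exposure is not below the comparator's.** It is tempting to take deaths and a 20% hold-out from the 3,000 patient-months and conclude that this study trains on less than the comparator did. That treats one side only. With the same constant death rates on both, exposure is 2,864 against 2,587 patient-months (17% per year) and 2,593 against 2,234 (45% per year). This study is then 11% to 16% larger, and an equal hold-out on both sides leaves the ratio unchanged.

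**Deaths are one target among several.** The sentence about 500 patients concerns alarms and unexpected interventions. Alarms may be numerous, and readmissions can recur. This stands, and it limits the point to mortality and any target with similarly few events.

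**Safeguards exist.** k-fold cross-validation and an external trial are planned, and the plan is open about the qualitative, budget-limited size. This softens the point without answering it. The cross-validation is described for tuning and robustness, with the test on unseen data assigned to the held-out part. The trial comes after implementation.

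**Cross-validation assesses a procedure.** A locked test set assesses one final model, which nested cross-validation does not. This is true, and it is the price of the fix.

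**Conclusion.** The point holds in a limited form. The assurance about 500 patients has no quantitative support in the documents. For mortality, a single hold-out of usual size gives an estimate too imprecise to use: about 4 to 39 test deaths across assumed fractions of 10% to 30%, and at 20% a 95% interval for sensitivity of 0.40–0.97 to 0.61–0.93.

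This rests on the general 17% to 45% first-year mortality applying here, a constant hazard, and a hold-out fraction that the plan does not state. Early clustering of deaths could raise the counts by an amount the documents do not give. Nothing here shows that the alarm-relevance model, readmissions, emergency visits or medication changes will have too few test events, or that 500 patients is the wrong number. A change to the test method is worth making because it recovers most of the lost precision from data already planned.

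**What to change.** No extra enrolment is needed. In Section 7:

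1. For mortality, and any target with similarly few events, estimate sensitivity, precision, C statistic and calibration by nested cross-validation grouped by patient, or leaving out one hospital at a time. Keep tuning in the inner loop, take one set of out-of-fold predictions for every patient, and use patient-level bootstrap intervals. All 44 to 129 deaths then contribute. Leaving out hospitals would also address the Section 5.2 aim of robustness in new hospitals.
2. Keep the held-out part for the alarm-relevance model and other targets with many events. State its fraction and the unit of the split.
3. Replace the assurance about 500 patients by the expected number of events and the expected interval width for each target, with the assumed rates shown.

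The cost is SAP text and computing time. For rare targets there would be no single locked model tested on untouched data within this study; the external trial already planned would test the locked model. At the low end of the mortality range the interval stays fairly wide (0.65–0.90), and the report should say so.

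### Section 7 names precision and sensitivity as the best measures for the unbalanced alarm problem, but the evaluation it commits to reports neither, nor the reduction in irrelevant alarms

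*Combined protocol and SAP*

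**What the plan says.** Section 7 (Statistical analysis plan and power calculation) expects most alarms to be annotated as irrelevant and few as relevant. It treats a two-class task as an option: "We could simplify the classification task by categorizing alarms as relevant or irrelevant, thus reducing it to a binary classification problem". It then states "In an unbalanced classification problem as in our case, the best measurements to assess model performance are precision and sensitivity" and defines both measures. It also describes a telemonitoring study of 308 heart failure patients in which accuracy was high but sensitivity very low, and presents this as a risk of misclassifying patients.

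The commitment on evaluation comes at the end of the section: "model performance in terms of accuracy will be evaluated by means of C statistic, the area under the receiver operating characteristic curve", together with a calibration plot. The Data Analysis row of the synopsis repeats it: "model performance in terms of accuracy will be evaluated by means of C statistic, area under the receiver operating characteristic curve". Fairness and bias are to be examined with "metrics such as statistical parity, group fairness, equalized odds, and predictive equality". Part of the data is kept out of training and validation "in order to test model performance on new data never seen by the algorithm".

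Section 5.2 gives the purpose of the alarm models: "Provide a relevance level for each new alarm by reducing the number of irrelevant alarms and thus fostering personalized follow-up". Objective B in the synopsis has the same aim. Section 4.1 gives the motive: clinicians review and discard many of the alarms that the present system raises.

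**The concern.** The plan says which measures suit its problem and then commits to others. The C statistic, the AUROC and the calibration plot are all computed without a decision threshold. They suit a graded relevance score, but they do not count alarms. For a two-class outcome the C statistic equals the AUROC, so the list in effect holds one discrimination measure and one calibration display.

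The modelling part of the primary endpoint asks a counting question: how many irrelevant alarms would no longer reach the clinician, and how many relevant ones would be lost with them? A report could follow the plan in full, show a good AUROC, a good calibration plot and satisfactory fairness results, and leave both parts unanswered. The plan's own account of the 308-patient study shows awareness that a good headline figure can hide poor sensitivity.

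**Working it through.** **Comparing the passages.** There is no planned figure to reproduce: 500 patients was chosen qualitatively, and no alpha, power, AUROC, threshold or share of relevant alarms is given.

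| Quantity | Called best in Section 7 | In the committed evaluation (Section 7, synopsis) | Needed for the aim in Section 5.2 |
|---|---|---|---|
| Overall sensitivity | yes | no | yes |
| Overall precision | yes | no | yes |
| Share of irrelevant alarms filtered | not mentioned | no | yes |
| C statistic / AUROC | no | yes | supportive |
| Calibration plot | no | yes | supportive |
| Between-group fairness metrics | no | yes | separate requirement of Section 5.2 |

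**How much one AUROC leaves open.** Every input here is an assumption, not a value from the documents: a two-class label, normally distributed scores with equal variance in both classes, AUROC 0.80 to 0.90, sensitivity 80% to 95%, and 2% to 20% of alarms relevant.

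- Separation of the two score distributions: d = √2 × Φ⁻¹(AUROC)
- Threshold: t = Φ⁻¹(1 − sensitivity) + d
- Share of irrelevant alarms below the threshold: Φ(t)
- False-positive rate: FPR = 1 − Φ(t)
- Share of relevant alarms below the threshold: 1 − sensitivity
- Precision, with p the share of alarms that are relevant: p × sensitivity / [p × sensitivity + (1 − p) × FPR]

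Example with AUROC 0.85 and sensitivity 0.80: d = 1.414 × 1.036 = 1.466; t = −0.842 + 1.466 = 0.624; Φ(0.624) = 0.734; FPR = 0.266.

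Share of irrelevant alarms below the threshold:

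| AUROC | Sensitivity 80% | 90% | 95% |
|---|---|---|---|
| 0.80 | 64% | 46% | 32% |
| 0.85 | 73% | 57% | 43% |
| 0.90 | 83% | 70% | 57% |

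Per 1,000 alarms, AUROC 0.85, 10% relevant (100 relevant, 900 irrelevant):

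| Sensitivity | Irrelevant below threshold | Relevant below threshold | Precision |
|---|---|---|---|
| 80% | 900 × 0.734 = 660 | 20 | 80/(80 + 240) = 25% |
| 90% | 900 × 0.573 = 516 | 10 | 90/(90 + 384) = 19% |
| 95% | 900 × 0.429 = 386 | 5 | 95/(95 + 514) = 16% |

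The AUROC is 0.85 in all three rows.

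Precision at 80% sensitivity, by share of relevant alarms:

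| AUROC | 2% | 5% | 10% | 20% |
|---|---|---|---|---|
| 0.80 | 4% | 10% | 20% | 35% |
| 0.85 | 6% | 14% | 25% | 43% |
| 0.90 | 9% | 20% | 35% | 55% |

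The AUROC fixes neither the trade-off actually chosen nor the precision that follows from it.

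**The case against.** **The precision and sensitivity sentence is sample-size rationale.** It leads to the statement that "the sample size for the present study has been determined qualitatively taking into consideration the reasons mentioned above". This is partly right, and on that reading the tension within Section 7 is weaker. But the sentence is worded as one about assessing performance in this study, and without it the gap against the aim in Section 5.2 remains.

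**The two lists may be complementary.** The plan nowhere says that only the measures in the later list will be reported. That is fair, but a measure described as best and then left out of the evaluation sentence, in both Section 7 and the synopsis, is not a commitment.

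**A graded relevance score needs no threshold.** The two-class task is only an option, and AUROC and calibration do suit a graded score. This stands as a reason to keep them. Counting filtered alarms still needs a cut-off.

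**The fairness metrics already require the rates.** This is the strongest point. Equalized odds needs true- and false-positive rates by group, from which the filtered and lost shares follow. The list is open and group fairness is undefined, so precision by group is possible too. The missing step is therefore smaller than it first looks. Even so, these are contrasts between groups; they could be reported as differences alone, they need a threshold that is not stated, and they do not oblige anyone to give overall figures.

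**Clinical effectiveness is left to a later trial.** True, and it limits the consequence. That trial compares clinical outcomes; it does not answer this study's own modelling endpoint.

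**The label rule and the clustered intervals go beyond the defect.** They are what makes the added measures usable. Without a label rule the counts cannot be formed, and a supervised two-class model would need one anyway. Each patient can contribute many alarms, so intervals that treat alarms as independent would tend to be too narrow.

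**Conclusion.** The concern holds. Nothing in Section 7 or the synopsis commits the study to overall sensitivity, overall precision or the reduction in irrelevant alarms, although Section 7 calls the first two the best measures and Section 5.2 makes the third the aim. This rests on the text alone.

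The size rests entirely on assumed values. Across AUROC 0.80 to 0.90 and sensitivity 80% to 95%, the share of irrelevant alarms filtered runs from 32% to 83%. Within AUROC 0.85 alone it runs from 43% to 73%, with 5% to 20% of relevant alarms lost. The exact figures would change with the score distributions; the fact that one AUROC is compatible with many operating points would not. This should be fixed, but the consequence is confined to how well the study answers its own modelling endpoint.

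**What to change.** In the evaluation paragraph of Section 7, with a matching sentence in the Data Analysis row of the synopsis, add for the alarm model:

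- overall sensitivity, overall precision, and the shares of irrelevant and of relevant alarms below the threshold, computed on the held-out data (the relevant share is one minus sensitivity, shown so that the loss is explicit);
- the rule that turns clinicians' annotations into relevant or irrelevant, written before the held-out data are analysed;
- a threshold fixed in the training data, stated in the report and used for the fairness metrics as well;
- 95% confidence intervals that allow for clustering of alarms within patients, for example from a bootstrap that resamples patients.

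Keep the AUROC, the calibration plot and the fairness metrics.

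The cost is a short paragraph, a synopsis sentence and modest analysis code. Annotations (Section 8.2.1) and held-out data are already planned, so no new patient data are needed. The real work is the label rule: Section 8.2.1 gives no annotation scale, and free-text annotations would have to be coded. The downside is that the results depend on the label rule and the threshold, and may look less favourable than an AUROC.
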